7.1 Subject data

7.1.1 Subject disposition

- Number of subjects screened
- Number of screening failures

This will be shown by analysis population for all subjects (FIP), by site (CSP) and by specialty (SPP).

- Observation period in days
 - Observation period will be derived from the end of study questionnaire as
observation period = Date of last patient – date of first patient +1
- Total number of patients in the observation period
- Actual number patients in the observation period (absolute and percentage of total number of patients)

This will be shown by analysis population for all investigators (FIP) and by site (SPP).

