6 ANALYSIS SETS

The allocation of subjects to analysis sets will be determined by the sponsor and the CRO on a per-subject basis immediately before data base lock.

Full eligible population (FEP)

The FEP population consists of all screened subjects, both successful and failed screens.

Full included population (FIP)

The FIP population consists of all successful screens.

Safety population (SAF)

The SAF population consists of all patients with a documented MRI/MRA procedure.

Population by country/site (CSP)

The CSP population consists of all successful screens in with known country/site.

Population by GBCA type (GBCAP)

The GBCA population consists of all subjects with known GBCA brand type.

Population by speciality (SPP)

The SPP population consists of all subjects examined for an ailment with known speciality.

Population by GFR rate (GFRP)

The GFR population consists of all subjects with known range of GFR rate.

Population by History of allergy (HISALP)

The history of allergy population consists of all subjects with known history of allergy status.

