7.1.2 Demographics and other baseline characteristics

Demographics and baseline characteristics will be analysed descriptively for all patients (FIP), by GBCA (GBCAP) and by site (SPP).

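### Screened and failed counts are assigned to sets that hold only successful screens, and five by-site analyses are assigned to the specialty set

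*SAP*

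**What the plan says.** SAP section 6 defines the sets that matter here:

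- FEP: "The FEP population consists of all screened subjects, both successful and failed screens".
- FIP: "The FIP population consists of all successful screens".
- CSP: "The CSP population consists of all successful screens in with known country/site".
- SPP: "The SPP population consists of all subjects examined for an ailment with known speciality".

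Section 7.1.1 lists two disposition counts, subjects screened and "Number of screening failures", and assigns them as follows: "This will be shown by analysis population for all subjects (FIP), by site (CSP) and by specialty (SPP". For the observation period and the patient counts that go with it, the same section says: "This will be shown by analysis population for all investigators (FIP) and by site (SPP". Section 7.1.2 assigns demographics "by GBCA (GBCAP) and by site (SPP". Section 7.1.3 (in two places) and section 7.1.4 (previous scans) also attach SPP to the by-site analysis. The disposition part of 7.1.1 and sections 7.1.6, 7.1.7, 7.1.8 and 7.3 attach CSP.

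**The concern.** There are two separate problems of set assignment.

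First, a count of screening failures can only be made in a set that contains them. FIP and CSP do not. FEP does, but no analysis in section 7 names it.

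Second, CSP is the country and site set, and SPP is the specialty set. Where a by-site analysis is run on SPP, a patient with no known specialty leaves that table but stays in the by-site tables run on CSP. Section 5.5 replaces no missing values, so the exclusion would stand.

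The study's primary objective is the pattern of contrast-agent use in routine practice, so readers will want to see who was screened and who was included at each site. Section 7 also plans exploratory ANOVA and chi-square comparisons between strata. Comparisons between sites would then rest on somewhat different patients in different sections of the same report.

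**Working it through.** The SAP gives no figure to reproduce. The check is one of set definitions, with illustrations where the SAP gives no count.

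**1. Screening failures.** Let S be the number of successful screens and F the number of failed screens. From section 6:

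- n(FEP) = S + F
- n(FIP) = S
- n(CSP) = successful screens with known country/site, so at most S

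Failures counted within FIP = 0, and within CSP = 0. The number screened within FIP = S, which is the number included. On FEP, the number screened = S + F, and failures = n(FEP) − n(FIP) = F.

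SPP carries no stated restriction to successful screens, so failures in the by-specialty table (Table 1.3) are not zero by definition. They would be counted only where a failed screen has a recorded specialty.

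For illustration, take S = 5400 (the enrolment ceiling in section 3.1) and an assumed failure proportion f, so that n(FEP) = 5400 / (1 − f):

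| Assumed f | Screened / failed on FEP | Literal result on FIP |
|---|---|---|
| 0% | 5400 / 0 | 5400 / 0 |
| 5% | 5684 / 284 | 5400 / 0 |
| 10% | 6000 / 600 | 5400 / 0 |

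**2. Set attached to each by-site analysis.**

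| SAP section | Content | Set |
|---|---|---|
| 7.1.1 | Screened and failed counts | CSP |
| 7.1.1 | Observation period and patient counts | SPP |
| 7.1.2 | Demographics and baseline | SPP |
| 7.1.3 | Diagnoses and reasons for contrast | SPP |
| 7.1.3 | Diagnostic precision and question category | SPP |
| 7.1.4 | Previous scans | SPP |
| 7.1.6 | Referral and repeat scans | CSP |
| 7.1.7 | Injection and scanning | CSP |
| 7.1.8 | Diagnostic impact | CSP |
| 7.3 | Adverse events | CSP |

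That is five SPP assignments in four sections. In 7.1.4 the same sentence gives SPP for site and CSP for country, although section 6 defines CSP for both.

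**3. Size of the denominator difference.** Assume that site is known for everyone and that SPP holds only included patients. If a proportion m has no known specialty, the by-site tables on SPP lose 5400 × m patients in total:

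- m = 0%: 0
- m = 1%: 54
- m = 5%: 270

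These values of m are assumptions. The loss at a single site could be larger or smaller than its share.

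**4. What is affected in the observation-period table.** The observation period and the total number of patients come from the end-of-study questionnaire and are investigator-level data (sections 3.2.2 and 7.1.1), so a missing patient specialty cannot alter them. Only the actual number of patients and its percentage of the total can change. With the numerator restricted to SPP, a site's percentage is multiplied by (1 − m), where m is that site's proportion with unknown specialty.

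**5. Text against table list.** Appendix 1 lists demographics by site (Table 3.2) and by specialty (Table 3.3). Section 7.1.2 provides only a by-site analysis, labelled SPP. Either the set label is wrong, or two items (site on CSP, specialty on SPP) were merged into one. The text does not say which.

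**The case against.** The strongest reply is that these are label slips which a competent programmer would see through. The disposition sentence says the counts are shown by analysis population, and the titles of Tables 1.1 to 1.3 couple disposition with the analysis populations. On that reading the tables list the size of every set, FEP included, and failures are visible as FEP minus FIP. This stands to the extent that a zero is not certain in the final output. A reader might infer that the disposition tables must always show zero failures. The documents do not support that, both for this reason and because SPP is not restricted to successful screens. It does not rescue the text, which names FIP and CSP and leaves FEP unnamed throughout section 7.

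A reader might also infer that the plan conceals selection at the sites. That goes too far. Section 7.1.1 separately reports the actual number of patients as a percentage of all patients in the observation period, overall and by site, and this bears directly on capture.

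On the by-site tables, referring specialty is a coded field with a category for other (section 3.2.1.4). Unknown specialty may therefore be rare, and SPP and CSP may nearly coincide. That is a fair limit on the size of the effect, but the inconsistency in the text remains.

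**Conclusion.** The point holds as an error in how analysis sets are assigned. Followed literally, section 7.1.1 gives zero failures and a screened count equal to the included count in Tables 1.1 and 1.2, whatever happened at screening. This follows from the definitions in section 6 and needs no assumption. It does not extend by definition to the by-specialty table.

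The five by-site assignments to SPP conflict with the definition of CSP and with its use elsewhere. Their effect equals the number of patients with unknown specialty, under the assumptions stated in the working. The SAP does not give that number, and it may be small.

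The study is descriptive with no a priori hypothesis. No controlled error rate is at stake, and the overall FIP estimates of pattern of use do not change. What is at stake is a usable account of screening and consistent by-site denominators.

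**What to change.** Three changes to the SAP text:

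1. In 7.1.1, report the numbers screened and failed on FEP: overall, by site within FEP where the site is known, and by specialty within FEP where the specialty is known.
2. In 7.1.1 (observation period), 7.1.2, 7.1.3 (both places) and 7.1.4, change the set attached to the by-site analysis from SPP to CSP.
3. In 7.1.2, add an analysis by specialty on SPP, so that Tables 3.2 and 3.3 are both supported by the text.

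The cost is a short SAP revision and changed population flags in the affected table programs. No new set or data item is needed. The changes should be made before subjects are allocated to analysis sets, which section 6 places immediately before database lock.

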7.1.2 Demographics and other baseline characteristics

Demographics and baseline characteristics will be analysed descriptively for all patients (FIP), by GBCA (GBCAP) and by site (SPP).

7.1.3 Diagnosis and reason for contrast media

The number and frequency of diagnoses (primary and secondary), diagnosis questions, main reason and specific reason for using contrast media will be analysed for all patients (FIP), by site (SPP) and by specialty (SPP). Additionally, the main reason for using contrast media will be shown by GBCA (GBCAP).

The precision of the diagnostic criteria (derived from the diagnostic text field on a scale from 0-3, 0=extremely vague, 1=approximate, 2=sufficiently defined, 3=very defined) and the categories of the diagnostic question (rule-in vs rule-out vs diagnosis refinement vs diagnosis clarification) will be analysed for all patients (FIP), by site (SPP), by specialty (SPP) and by GBCA (GBCAP). Precision of diagnosis will be an derived from existing data and will be performed by GEHC

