2 STUDY OBJECTIVES AND ENDPOINTS

2.1 Study objectives

Primary objectives:

The primary objective of the GBCA observational study, will be to prospectively collect data on the pattern of use for GBCA in real-life setting with special reference to Clariscan after its commercial launch in Europe.

Secondary objectives:

The study will look at the effectiveness and safety profile of GBCAs including Clariscan in clinical practice

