5.8 Statistical significance (p-values)

A p-value of <0.05 will be declared as statistically significant.

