7 STATISTICAL METHODS

All continuous variables will be summarized using the following descriptive statistics: n (non-missing sample size), mean, standard deviation, median, minimum and maximum. The frequency and percentages (based on the non-missing sample size) will be reported for categorical measures. Data that will be listed will be sorted by country, site and subject.

For the comparison of endpoints in stratified analyses (e.g. by country, by GBCA etc.) explorative statistical tests will be applied (ANOVA for continuous endpoints, Chi-Square tests for categorical endpoints) if feasible.

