Table	8.8	Precision of the diagnostic criteria by GBCA
Table	8.9	Categories of diagnostic question
Table	8.10	Categories of diagnostic question by site
Table	8.11	Categories of diagnostic question by specialty
Table	8.12	Categories of diagnostic question by GBCA
Figure	8.13	Bar chart of mean change in radiological diagnosis by quality of referral notes
Figure	8.14	Bar chart of mean change in increase of confidence by quality of referral notes
Table	8.15	Quality of CE-MRI and CE-MRA
Table	8.16	Quality of CE-MRI and CE-MRA by age
Table	8.17	Quality of CE-MRI and CE-MRA by country
Table	8.18	Quality of CE-MRI and CE-MRA by site
Table	8.19	Quality of CE-MRI and CE-MRA by GBCA
Figure	8.20	Bar chart of mean quality of image by change in radiological diagnosis
Figure	8.21	Bar chart of mean quality of image by change in confidence for the diagnosis
Table	9.1	Staffing equipment
Table	9.2	Staffing equipment by country
Table	10.1	User satisfaction
Table	10.2	User satisfaction by country
Table	10.3	User satisfaction by GBCA
Table	11.1.1	Number of patients with adverse events by SOC and PT
Table	11.1.2	Number of patients with serious adverse events by SOC and PT
Table	11.1.3	Number of patients with adverse events by causality, SOC and PT
Table	11.1.4	Number of patients with adverse events by treatment, SOC and PT
Table	11.1.5	Number of patients with adverse events by severity, SOC and PT
Table	11.1.6	Number of patients with adverse events by time to onset, SOC and PT
Table	11.2.1	Number of patients with adverse events by site, SOC and PT
Table	11.2.2	Number of patients with serious adverse events by site, SOC and PT
Table	11.2.3	Number of patients with adverse events by site, causality, SOC and PT
Table	11.2.4	Number of patients with adverse events by site, treatment, SOC and PT
Table	11.2.5	Number of patients with adverse events by site, severity, SOC and PT
Table	11.2.6	Number of patients with adverse events by site, time to onset, SOC and PT
Table	11.3.1	Number of patients with adverse events by site, SOC and PT
Table	11.3.2	Number of patients with serious adverse events by country, SOC and PT
Table	11.3.3	Number of patients with adverse events by country, causality, SOC and PT
Table	11.3.4	Number of patients with adverse events by country, treatment, SOC and PT
Table	11.3.5	Number of patients with adverse events by country, severity, SOC and PT
Table	11.3.6	Number of patients with adverse events by country, time to onset, SOC and PT

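### SAP 7.1.3 has a judgement-based 0-3 precision score assigned from free text and analysed by brand and site, but specifies no masking of the scorers

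*SAP*

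**What the plan says.** Section 7.1.3 defines a precision score that is "derived from the diagnostic text field on a scale from 0-3, 0=extremely vague, 1=approximate, 2=sufficiently defined, 3=very defined". On who does this, and from what, it says "Precision of diagnosis will be an derived from existing data and will be performed by GEHC". The same section has the score analysed overall, by site, by specialty and by GBCA. Appendix 1 plans Tables 8.5 to 8.8 for it, and Table 8.8 is "Precision of the diagnostic criteria by GBCA".

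For stratified comparisons, section 7 says that "explorative statistical tests will be applied (ANOVA for continuous endpoints, Chi-Square tests for categorical endpoints) if feasible". Section 5.8 adds that "A p-value of <0.05 will be declared as statistically significant", and section 5.7 rules out adjustment for multiple testing.

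The SAP contains no statement on masking the scorers to brand, site or post-scan results. It also gives no scoring rules beyond the four short anchors, no second scorer, no agreement check, and no timing of the scoring relative to database lock or to the interim analysis in section 5.2.

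**The concern.** The score is a judgement. With anchors of one or two words and no rubric, two careful people could place the same entry one level apart. If the scorer knows which brand was used or which site sent the record, that knowledge can influence borderline calls. The order of scoring matters as well: if records are worked through site by site, a gradual change in the scorer's standard will line up with site, and with brand wherever brand use differs between sites.

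The SAP itself creates this variable and names who assigns it, and section 1.2 says that it holds information the protocol does not cover. So this is the natural place to state the conditions of scoring. At stake is whether any difference in Tables 8.6 to 8.8 can be read as a difference in how diagnoses were written down, and not in how they were graded.

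**Working it through.** The SAP gives no sample-size, power or variance figure for this score, so there is nothing to reproduce. The check has two parts.

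**Part 1: what the text supports**

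- *Who scores:* GEHC, for precision only (7.1.3). The SAP does not say who assigns the diagnostic-question categories (rule-in, rule-out and so on) named in the same paragraph.
- *What is scored:* the diagnostic text field. Section 3.2.1.3 lists the diagnosis for which the scan was indicated, which is the likely source, but 7.1.3 does not name the variable.
- *When:* after collection, since the data already exist.
- *Compared across:* site (Table 8.6), specialty (8.7) and GBCA (8.8). Table 8.5 is overall and compares nothing.
- *Masking:* not mentioned anywhere in the SAP.

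**Part 2: how small a scoring shift could reach p<0.05 (illustration only)**

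From the SAP: up to 5400 patients (3.1) and a threshold of 0.05 (5.8; two-sided is assumed). Assumed: no true difference, the score compared as a mean between one brand and all others, a brand share of 10% to 50%, an SD of 0.7 to 0.9, and a scorer who shifts one brand's mean by b points.

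Formulas:
- SE = SD × √(1/n₁ + 1/n₂)
- P(p<0.05) ≈ Φ(b/SE − 1.96)
- shift giving 80% probability = (1.96 + 0.84) × SE

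Least sensitive case at N = 5400 (share 10%, SD 0.9): n₁ = 4860, n₂ = 540, SE = 0.9 × √(1/4860 + 1/540) = 0.0408. For b = 0.1, 0.1/0.0408 − 1.96 = 0.49, so the probability is 0.69. The 80% shift is 2.80 × 0.0408 = 0.114.

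Most sensitive case (share 50%, SD 0.7): SE = 0.7 × √(2/2700) = 0.0191. For b = 0.1 the probability is 0.999. The 80% shift is 0.053.

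| Total N | P(p<0.05) with b = 0.1 | Shift giving 80% |
|---|---|---|
| 5400 | 0.69 to 0.999 | 0.05 to 0.11 |
| 2700 | 0.41 to 0.96 | 0.08 to 0.16 |

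A middle case puts this in terms of records. With 2700 per group and SD 0.8, SE = 0.8 × √(2/2700) = 0.0218 and 1.96 × SE = 0.0427. Grading 1/0.0427, or about 1 record in 23, one level higher in one group is then enough to reach the threshold. Grading 1 record in 10 higher shifts the mean by 0.1, which is 0.1/0.0218 = 4.6 standard errors.

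This shows only that, at this sample size, small tendencies are detectable. It does not show that such a tendency is likely. Brand shares are unknown, the dose formula in 7.1.7 implies more than two brands, and a four-level score may be tested by chi-square instead of as a mean.

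**The case against.** The strongest reply is that the SAP is silent on masking. A reader might infer that it orders unmasked scoring from a database showing brand and site. It does not say that, and a protocol or coding manual that is not shown could cover the procedure. This stands: the point is that no masking is specified, not that scoring is known to be unmasked.

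Second, a reader might infer that an interested party is grading its own product, because section 2.1 describes the primary objective as "with special reference to Clariscan after its commercial launch in Europe". That phrase concerns pattern of use. The available text neither defines GEHC nor links it to a brand, and no contrast of Clariscan against other agents is specified for this score. This stands too. The argument does not need a commercial motive, because any scorer who sees brand or site can be influenced.

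Third, the score is probably not a product outcome. The contrast agent cannot alter how precisely a pre-scan diagnosis was worded, and the diagnostic-impact variables are defined separately (3.2.1.6, 3.2.1.7) and analysed in 7.1.8. A true brand gap would mainly reflect referral mix or site. This limits the stakes. It also means that the scorer loses nothing essential by not seeing the brand.

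Fourth, the study is descriptive and its tests are exploratory, to be run where feasible. That lowers the weight of the point but does not remove it, since 5.8 still labels results below 0.05 as significant.

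**Conclusion.** The point holds as a modest risk of detection bias in a secondary descriptor: a judgement-based score, compared by brand and site, with no masking specified. It is firmest for Tables 8.6 to 8.8. It extends to the by-site, by-specialty and by-GBCA tables of the diagnostic-question categories (8.10 to 8.12) only if those are also coded from text, which the SAP does not say.

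Two stronger conclusions are not supported. The documents do not show a bias in a product-effect outcome. Nor would the damage be permanent: the source text is stored, so it can be rescored from a masked extract later.

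The size cannot be fixed from the SAP. Under the assumed shares and SDs, a shift of about 0.05 to 0.11 point at 5400 patients, or 0.08 to 0.16 at 2700, would give an 80% chance of p<0.05 with no true difference. The change is a cheap improvement and does not bear on the primary objective.

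**What to change.** Add to 7.1.3 that precision scoring is done on an extract holding only the diagnostic text field and a random record ID, in random order, with brand, site, country and all post-scan variables removed, and that the scores are locked before being merged back. Apply the same rule to the diagnostic-question categories if they are coded from text. If scores have already been assigned without masking, for example for the interim analysis, rescore from such an extract.

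The cost is one extra data extract, one merge step and a sentence or two in the SAP, with no new data or staff. There are two limits. Scorers lose any context outside the text field, so some entries may be harder to grade. Masking also does nothing for the reliability of the score; a short written rubric and a second scorer with reported agreement would address that, but they are separate additions with their own cost.

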7.1.4 Medical history

The number and frequency of comorbidities, pre-medications, concomitant medications and patients with previous scans will be analysed for all patients (FIP) and by GBCA (GBCAP). Additionally, number and frequency of previous scans will be shown by site (SPP) and by country (CSP). For patients with allergies, further details about the allergy status will be tabulated. For patients with renal impairment eGFR and the renal replacement status will be analysed.

A patient is defined to have a previous scan if either the referral type is a repeat scan or any other image scan has been performed before the contrast enhanced MR scan session in relation to the illness under investigation.

7.1.5 Funding

The number and frequency of the source of funding, full or partially self funding and what is being paid for will be analysed for all patients (FIP), by country (CSP), by specialty (SPP) and by GBCA (GBCAP).

Additionally type of funding will be stratified by quality of referral.

7.1.6 Referral

The number and frequency of the quality of referral notes, quality stratified by type of referral, quality of referral notes stratified by seniority, type of referral, seniority, specialty, repeat scans, reason for repeat scans and reason for repeat scans stratified by type of referral will be analysed for all patients (FIP), by site (CSP), and by country (CSP).

Repeat scans, reason for repeat scans and reason for repeat scans stratified by type of referral will additionally be analysed for all patients (FIP), by site (CSP), by country (CSP), by specialty (SPP) and by GBCA type (GBCAP).

